## 6.5. Baseline and Other Summaries and Analyses

Demographic data collected at screening will be reported as part of the standard baseline summary tables. A breakdown of demographic data will be provided for age, race, weight, body mass index, and height. Each will be summarized by gender and all participants in accordance with the sponsor reporting standards.

### 6.5.1. Study Conduct and Participant Disposition

Subject evaluation groups will show end of study subject disposition and will show which subjects were analyzed for pharmacokinetics, as well as for safety (adverse events and

laboratory data). Frequency counts will be supplied for subject discontinuation(s) by treatment. Data will be reported in accordance with the sponsor reporting standards.

### **6.5.2. Study Treatment Exposure**

Not applicable.

### **6.5.3. Concomitant Medications and Nondrug Treatments**

All concomitant medication(s) as well as non-drug treatment(s) will be provided in the listings.

## **6.6. Safety Summaries and Analyses**

A set of summary tables split by treatment will be produced to evaluate any potential risk associated with the safety and toleration of administering ritlectinib as PO solution, MR1, or MR2 formulation.

### **6.6.1. Adverse Events**

Adverse events will be reported in accordance with the sponsor reporting standards.

### **6.6.2. Laboratory Data**

Laboratory data will be listed and summarized by treatment in accordance with the sponsor reporting standards. The baseline measurement is the pre-dose measurement on Day -1.

### **6.6.3. Vital Signs**

For each planned time point, baseline values and change from baseline values in Periods 1-3 and Period 4 will be summarized with descriptive statistics (using sponsor default standards) as appropriate.

These data will be listed in accordance with the sponsor reporting standards. The thresholds used in the categorical summarization of vital signs data are presented in the [Appendix 1](#).

### **6.6.4. Electrocardiograms**

For each planned time point, baseline values and change from baseline values in Periods 1-3 and Period 4 will be summarized with descriptive statistics (using sponsor default standards) as appropriate.

These data will be listed in accordance with the sponsor reporting standards. The thresholds used in the categorical summarization of vital signs data are presented in the [Appendix 1](#).

## **7. INTERIM ANALYSES**

### **7.1. Introduction**

No formal interim analysis will be conducted for this study. As this is a sponsor-open study, the sponsor may conduct unblinded reviews of the data during the course of the

study for the purpose of safety assessment, facilitating PK/PD modeling, and/or supporting clinical development.

## **7.2. Interim Analyses and Summaries**

Available safety and PK data may be reviewed.

## APPENDICES

### Appendix 1. Categorical Classes for ECG and Vital Signs of Potential Clinical Concern

#### Categories for QTcF

Degree of Prolongation	Mild (msec)	Moderate (msec)	Severe (msec)
Absolute value	>450-480	>480-500	>500
Increase from baseline		>30-60	>60

#### Categories for PR and QRS

PR (ms)	$\geq 300$	
PR (ms) increase from baseline	Baseline $>200$ and $\geq 25\%$ increase	Baseline $\leq 200$ and $\geq 50\%$ increase
QRS (ms)	$\geq 140$	
QRS (ms) increase from baseline	$\geq 50\%$ increase	

#### Categories for Vital Signs

Systolic BP (mm Hg)	$<90$	
Systolic BP (mm Hg) change from baseline	decrease $\geq 30$	increase $\geq 30$
Diastolic BP (mm Hg)	$<50$	
Diastolic BP (mm Hg) change from baseline	decrease $\geq 20$	increase $\geq 20$
Supine pulse rate (bpm)	$<40$	$>120$

Measurements that fulfill these criteria are to be listed in the clinical study report.

## Appendix 2. Example SAS Code for Analyses

Examples of the PROC MIXED code is provided below.

We start from the dataset ds with the following letter codes for the treatments

A = ritlecitinib 100 mg PO solution  
 B = ritlecitinib 100 mg (2 × 50 mg) MR1 capsules  
 C = ritlecitinib 100 mg (2 × 50 mg) MR2 capsules

B,fed = ritlecitinib 100 mg (2 × 50 mg) MR1 capsules under the fed state  
 C,fed = ritlecitinib 100 mg (2 × 50 mg) MR2 capsules under the fed state

For analysis of bioavailability, we use a subset of data (ds1) that does not include period 4 (ie, treatments B,fed and C,fed).

A = ritlecitinib 100 mg PO solution  
 B = ritlecitinib 100 mg (2 × 50 mg) MR1 capsules  
 C = ritlecitinib 100 mg (2 × 50 mg) MR2 capsules

We calculate contrasts 'A vs B' and 'A vs C'

proc mixed data=ds1;

```
class seq period trt subject;
model l&var=seq period trt/ ddfm=KR;
random subject(seq) ;
lsmeans trt;
estimate 'A vs B ' trt -1 1 0 /cl alpha=0.1;
estimate 'A vs C ' trt -1 0 1 /cl alpha=0.1;
ods 'Estimates' out=est&var;
ods 'lsmeans' out=ls&var;
ods 'covparms' out=cov&var;
ods 'tests3' out=tst&var;
run;
```

For analysis of food effect, we use a subset of data (ds2) that includes relevant doses

B = ritlecitinib 100 mg (2 × 50 mg) MR1 capsules  
 C = ritlecitinib 100 mg (2 × 50 mg) MR2 capsules

B,fed = ritlecitinib 100 mg (2 × 50 mg) MR1 capsules under the fed state  
 C,fed = ritlecitinib 100 mg (2 × 50 mg) MR2 capsules under the fed state

We calculate contrasts of interest ('B vs B,fed ' and 'C vs C,fed ') without adjustment for period effect.

```
proc mixed data=ds2;
  class seq trt subject;
  model l&var=seq trt/ ddfm=KR;
  random subject(seq) ;
  lsmeans trt;
  estimate 'B vs B,fed' trt -1 0 1 0 /cl alpha=0.1;
  estimate 'C vs C,fed' trt 0 -1 0 1 /cl alpha=0.1;
  ods 'Estimates' out=est&var;
  ods 'lsmeans' out=ls&var;
  ods 'covparms' out=cov&var;
  ods 'tests3' out=tst&var;
run;
```

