4. STUDY DESIGN

4.1. Overall Design

This is a single dose, open-label randomized, 4-period, 6-sequence crossover study in a single cohort of approximately 12 healthy male and/or female participants randomized to one of the sequences (containing 1 solution and 2 MR [MR1 and MR2] capsule formulations of ritlecitinib) displayed in Table 2 where the treatment names A; B & C are representative. The first 3 periods are under fasted condition and the fourth period is under fed condition to

investigate food effect on the PK of modified release formulations MR1 and MR2. Dosing in each treatment period will be separated by at least 3 days to minimize any carryover effect. The study includes standard inpatient monitoring of study participants following single oral doses. Standard safety laboratory tests and urinalysis both before and after dosing will assess participant safety, while intensive blood draws following ritlecitinib administration will provide PK exposure data to characterize the relative bioavailability and absorption rate from different formulations. Normal venous PK blood samples for PK analysis will be collected pre-dose and at times specified in the SoA. For a given participant, the total study duration from screening to follow-up phone call will be between approximately 8 and 11 weeks. Participants may be discharged between periods at the discretion of PI.

Participants who discontinue prior to completion of the study for reasons unrelated to safety may be replaced at the discretion of the PI and the sponsor. Participants withdrawn for safety reasons will not be replaced.

Table 2. Study Design and Treatments

Sequence	Period 1	Period 2	Period 3	Period 4
1 (n=2)	A	В	С	B, fed
2 (n=2)	В	С	A	B, fed
3 (n=2)	С	A	В	B, fed
4 (n=2)	A	В	С	C, fed
5 (n=2)	В	С	A	C, fed
6 (n=2)	С	A	В	C, fed

Treatment A: ritlecitinib 100 mg PO solution

Treatment B: ritlecitinib 100 mg (2×50 mg) MR1 capsules Treatment C: ritlecitinib 100 mg (2×50 mg) MR2 capsules

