9.5. Sample Size Determination

A sufficient number of participants will be screened to achieve 12 participants randomly assigned to study interventions such that exactly 2 participants will be enrolled to each of the 6 sequences. The sample size is empirically selected and is not based on statistical power calculation.

Analyses of data from studies B7981022, B7981029, and B7981030 suggest a within-participant standard deviation of 0.117 for log (AUC $_{inf}$) and within-participant standard deviation of 0.226 for log (C_{max}). The sample size of approximately 12 participants has been chosen.

The following table (Table 5) presents the reference boundaries and width of the confidence intervals for a range of estimates of the means ratio for pairs of treatments (Test vs Reference). The calculation assumes the selection of the default value (80%) of the tolerance parameter in the conventional calculation¹. The values of within-participant standard

deviations (standard deviation of 0.117 for log (AUC_{inf}) and standard deviation of 0.226 for log (C_{max})) and corresponding widths of the confidence intervals were used. The width of the confidence intervals for fed versus fasted comparison is larger because only half of the participants contribute observations for this comparison.

Table 5. Expected Widths of the 90% Confidence Intervals (With 80% Tolerance Probability) for Different Possible Estimated Effects of ritlecitinib MR1 and MR2 Formulations in Fasted and Fed Conditions on PK Parameters

Estimated	n=6				n=12				n=18			
ratio of means	AUC: a			AUC _{inf} C _{max}		AUCinf		Cmax				
	90% CI	CI width	90% CI	CI width	90% CI	CI width	90% CI	CI width	90% CI	CI width	90% CI	CI width
	MR/solution											
0.1	(0.08,0.12)	0.03	(0.07,0.14)	0.06	(0.09,0.11)	0.02	(0.08,0.12)	0.04	(0.09,0.11)	0.02	(0.09, 0.12)	0.03
0.2	(0.17,0.24)	0.07	(0.15, 0.27)	0.13	(0.18,0.22)	0.04	(0.17,0.24)	0.08	(0.19, 0.22)	0.03	(0.17,0.23)	0.06
0.3	(0.25, 0.35)	0.10	(0.22,0.41)	0.19	(0.27,0.33)	0.06	(0.25, 0.36)	0.12	(0.28, 0.32)	0.05	(0.26, 0.35)	0.09
0.4	(0.34,0.47)	0.13	(0.29, 0.55)	0.26	(0.36,0.44)	0.08	(0.33,0.48)	0.15	(0.37,0.43)	0.06	(0.35,0.46)	0.12
0.5	(0.42,0.59)	0.17	(0.36,0.69)	0.32	(0.45,0.55)	0.10	(0.41,0.61)	0.19	(0.46,0.54)	0.08	(0.43,0.58)	0.15
0.6	(0.51,0.71)	0.20	(0.44,0.82)	0.39	(0.54,0.66)	0.12	(0.50,0.73)	0.23	(0.56,0.65)	0.09	(0.52,0.70)	0.18
0.7	(0.59,0.83)	0.23	(0.51,0.96)	0.45	(0.63,0.77)	0.14	(0.58, 0.85)	0.27	(0.65, 0.76)	0.11	(0.60,0.81)	0.21

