## 6.2. Secondary Endpoint(s)

- *PK parameters of ritlecitinib (fed):  $C_{max}$ ,  $AUC_{inf}$  (if data permit), otherwise  $AUC_{last}$*

By the design of the trial, all of the observations made in the fed state are positioned in the single treatment periods and therefore the evaluation of the food effect is potentially confounded by the period effect. We assume that the magnitude of the food effect is much larger than the magnitude of the period effect and will be able to support this assumption by estimating the magnitude of the period effect for periods 1-3 in the relative bioavailability analysis described in [Section 6.1](#).

The analysis will be based on the subset of data observed for the following MR treatments:

B = ritlecitinib 100 mg (2 × 50 mg) MR1 capsules under the fasted state  
 C = ritlecitinib 100 mg (2 × 50 mg) MR2 capsules under the fasted state

B,fed = ritlecitinib 100 mg (2 × 50 mg) MR1 capsules under the fed state  
 C,fed = ritlecitinib 100 mg (2 × 50 mg) MR2 capsules under the fed state

Natural log transformed  $AUC_{inf}$  (if data permit),  $AUC_{last}$  and  $C_{max}$  will be analyzed using a mixed effect model with sequence and treatment as fixed effects and subject within sequence as a random effect. Estimates of the adjusted mean differences (Test-Reference) and corresponding 90% confidence intervals will be obtained from the model. The adjusted mean differences and 90% confidence intervals for the differences will be exponentiated to provide estimates of the ratio of adjusted geometric means (Test/Reference) and 90% confidence intervals for the ratios.

Note that in this analysis the period is not included as a fixed effect. The mixed effects model will be implemented using SAS Proc Mixed, with REML estimation method and Kenward-Roger- degrees of freedom algorithm. The illustrative SAS code is presented in the [Appendix 2](#).

For food effect assessment, ritlecitinib MR1 and MR2 in fasted state are the Reference treatments while ritlecitinib MR1 and MR2 administered in fed state are Test treatments.

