Similarly to the analysis in [Section 6.1](#), the residuals from the model will be examined for normality and the presence of outliers via visual inspection of plots of residuals vs predicted values and normal probability plots of residuals but these will not be included in the clinical study report. If there are major deviations from normality or outliers then the effect of these on the conclusions will be investigated through alternative transformations and/or analyses excluding outliers. Justification for any alternative to the planned analysis will be given in the report of the study.

A listing of the descriptive and graphical summaries for PK parameters is presented in [Section 6.4](#).

In addition, for the parameters  $AUC_{inf}$  (if data permit),  $AUC_{last}$  and  $C_{max}$ , a listing of the individual subject ratios (Test/Reference) will also be provided. Box and whisker plots for individual subject parameters ( $AUC_{inf}$ ,  $AUC_{last}$  and  $C_{max}$ ) will be presented by treatment and overlaid with geometric means.

- *Assessment of AEs, clinical laboratory tests, vital signs and 12-lead ECG*

For the secondary endpoint concerning safety, adverse events, laboratory data, vital signs, ECG data, and other safety data will be listed and summarized in accordance with the sponsor reporting standards as described in [Section 3.5](#).

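### With the treatment codes the SAP declares, its example food-effect contrasts estimate MR2/MR1 ratios, not the fed/fasted ratios defined in SAP 6.2

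*SAP*

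**What the plan says.** SAP 6.2 defines the food effect within each formulation: "For food effect assessment, ritlecitinib MR1 and MR2 in fasted state are the Reference treatments", with the fed administrations as Test. The model has sequence and treatment as fixed effects and participant within sequence as a random effect. Differences are Test minus Reference and are exponentiated to ratios with 90% confidence intervals. For implementation, 6.2 sends the reader to Appendix 2 ("The illustrative SAS code is presented in the" appendix).

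Appendix 2 opens: "We start from the dataset ds with the following letter codes for the treatments". It then lists A, B, C, `B,fed` and `C,fed`. The food-effect block uses the subset `ds2`, which holds the four MR codes. `trt` is a CLASS variable, and there is no ORDER= option, format or recoding. The two contrasts are:

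- "estimate 'B vs B,fed' trt -1 0 1 0 /cl alpha=0.1"
- "estimate 'C vs C,fed' trt 0 -1 0 1 /cl alpha=0.1"

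No other place in the SAP or protocol gives contrast coefficients for this analysis.

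**The concern.** The coefficients in an ESTIMATE statement attach to the levels of `trt` by position, so they have no meaning until the level order is known. The printed vectors need the order B, C, B,fed, C,fed. Nothing in the code sets that order, and the declared codes do not sort into it.

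The food effect is the first secondary objective. If a programmer uses the template with the declared codes, both reported food-effect ratios and their intervals describe a comparison of the two formulations, under labels that say fed versus fasted.

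**Working it through.** **Inputs.** Codes, CLASS statement and vectors come from SAP Appendix 2. The design is SAP Table 2: 12 participants, two per sequence. Dropping treatment A leaves 12 × 3 = 36 records. Protocol 9.5 says earlier studies "suggest a within-participant standard deviation of 0.117 for log" AUCinf, and gives 0.226 for log Cmax. The default level order (sorted formatted values when ORDER= is absent) is a property of the software and is not stated in the documents. The SAS block itself was not run. The same model was fitted in other software.

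**Step 1: the plan's own reading.** With levels ordered B, C, B,fed, C,fed, the vector (-1, 0, 1, 0) is B,fed − B and (0, -1, 0, 1) is C,fed − C. Both match their labels and SAP 6.2.

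**Step 2: the declared codes, sorted.** The order is B; B,fed; C; C,fed.

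| Printed vector | Label | What it estimates | Ratio |
|---|---|---|---|
| -1 0 1 0 | B vs B,fed | C − B | MR2/MR1, fasted |
| 0 -1 0 1 | C vs C,fed | C,fed − B,fed | MR2/MR1, fed |

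Both contrasts are estimable in this design.

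**Step 3: size of the error.** Write each code for its geometric mean.

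- Row 1, returned over intended: (C/B) ÷ (B,fed/B) = C/(B,fed).
- Row 2, returned over intended: (C,fed/B,fed) ÷ (C,fed/C) = C/(B,fed).

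The factor is the same in both rows. It equals 1 only if MR2 fasted and MR1 fed have equal exposure.

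Numerical check with assumed means B 0.60, C 0.30, B,fed 0.54, C,fed 0.36:

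| | Row 1 | Row 2 |
|---|---|---|
| True fed/fasted | 0.54/0.60 = 0.90 | 0.36/0.30 = 1.20 |
| Printed vectors, sorted levels | 0.30/0.60 = 0.500 | 0.36/0.54 = 0.667 |
| Printed vectors, order B, C, B,fed, C,fed | 0.90 | 1.20 |
| Vectors (-1 1 0 0) and (0 0 -1 1), sorted levels | 0.90 | 1.20 |

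The factor is 0.30/0.54 = 0.556 in both rows.

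Protocol 2.2.4.1.1 reports a Cmax reduction of about 32% with food for a 100 mg capsule, so take fed/fasted = 0.68 for both MR forms (assumed). Each row then returns the fasted MR2/MR1 ratio:

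- MR2/MR1 = 1.0 (assumed): rows read 1.00 and 1.00; factor 1/0.68 = 1.47.
- MR2/MR1 = 0.5 (assumed): rows read 0.50 and 0.50; factor 0.5/0.68 = 0.74.

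**Step 4: precision.** Every participant has both B and C fasted, and six have each fed treatment. With within-participant SD σ:

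- C − B: variance 2σ²/12 = σ²/6.
- B,fed − B, and likewise C,fed − C: σ²(1/6)(1 + 1/2) + (1/4)(σ²/6) = 7σ²/24.
- C,fed − B,fed: 2 × σ²(1/6)(1 + 1/2) = σ²/2.

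| Parameter | σ | SE returned, row 1 | SE returned, row 2 | SE intended, each row |
|---|---|---|---|---|
| AUCinf | 0.117 | 0.048 | 0.083 | 0.063 |
| Cmax | 0.226 | 0.092 | 0.160 | 0.122 |

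The fitted model gave the same SEs, and they did not change for between-participant SDs from 0.1 to 5.

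**Step 5: other level orders.** Under ORDER=DATA, with rows sorted by participant and period, the result depends on the first participant's sequence:

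| First sequence | Level order | Printed vectors |
|---|---|---|
| 1 or 2 | B, C, B,fed, C,fed | correct |
| 3 | C, B, B,fed, C,fed | wrong |
| 4 or 5 | B, C, C,fed, B,fed | wrong |
| 6 | C, B, C,fed, B,fed | right quantities, labels swapped |

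**Step 6: control.** In the bioavailability block A, B, C sort as written, so (-1, 1, 0) and (-1, 0, 1) give B/A and C/A as intended.

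**The case against.** The governing text is right. SAP 6.2 and protocol 9.3.1 both make fed the Test and fasted the Reference, and the contrast labels name the intended pairs. The code is offered as an illustration, and protocol 4.1 describes the design table as one "where the treatment names A; B & C are representative". The protocol's amendment summary explains that wording by a discrepancy with the randomization code, so the literal strings may never reach the analysis dataset. Appendix 2 also lists the treatments just above the block in the order the vectors need. Several outputs could expose a mismatch: the LSMEANS from the same call, the box plots with geometric means, the geometric means by treatment (SAP 6.4), and the planned listing ("a listing of the individual subject ratios (Test/Reference) will also be provided"). The study is exploratory, with no formal test, and a wrong table can be rerun. The case in which the food effect vanishes assumes equal fasted Cmax for products releasing over 6–8 and 13–15 hours, which the documents give no reason to expect.

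Most of this stands as a limit on the harm. It does not make the code right. A list in prose does not set CLASS order. If the analysis codes differ from the declared ones, the mapping has to be stated, because positional coefficients cannot be used without it. The SAP plans no check of the model contrasts against the other outputs.

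**Conclusion.** The concern holds. Read with the codes it declares and the procedure's default ordering, the example code gives MR2/MR1 ratios, fasted and then fed, in place of the two food-effect ratios. Both estimates are wrong by the factor (MR2 fasted)/(MR1 fed), and the standard errors are about 24% too small in row 1 (0.048 against 0.063) and 31% too large in row 2 (0.083 against 0.063).

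Two conditions apply: the declared strings are the formatted values of `trt`, and no ordering is imposed elsewhere. The size of the bias in this trial is unknown, since the documents give no MR1 or MR2 exposures; the ratios shown rest on assumed means. The definition in SAP 6.2 and the primary bioavailability analysis are sound. This should be corrected before the template is used.

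**What to change.** With the declared codes, replace the two lines by:

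- `estimate 'B,fed vs B' trt -1 1 0 0 /cl alpha=0.1;`
- `estimate 'C,fed vs C' trt 0 0 -1 1 /cl alpha=0.1;`

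Alternatively, keep the printed vectors and state a recoding of `trt` whose formatted values sort as B, C, B,fed, C,fed, for example numeric or prefixed codes. ORDER=DATA alone should not be relied on (Step 5). Adding the E option to each ESTIMATE statement prints the coefficients by level, so the order can be confirmed in the output.

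The cost is two lines of example code or one sentence in the SAP. Design, data collection and the analysis defined in SAP 6.2 do not change.

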### Appendix 3. List of Abbreviations

Abbreviation	Term
Abs	absolute
AE	adverse event
AUC	area under the curve
AUC inf	area under the plasma concentration-time profile from time 0 extrapolated to infinite time
AUC last	area under the plasma concentration-time profile from time 0 to the time of the last quantifiable concentration
BA	bioavailability
BE	bioequivalence
BLQ	below the limit of quantitation
BOCF	baseline observation carried forward
BP	blood pressure
bpm	beats per minute
CDARS	Clinical Data Analysis and Reporting System (of US Food and Drug Administration)
CI	confidence interval
CL/F	Apparent clearance after oral dose
C max	maximum observed concentration
CMH	Cochran-Mantel-Haenszel
CRF	case report form
CSR	clinical study report
DMC	data monitoring committee
EAC	event adjudication committee
ECG	electrocardiogram
E-DMC	external data monitoring committee
FAS	full analysis set
FDA	Food and Drug Administration (United States)
GCP	Good Clinical Practice
GMC	geometric mean concentration
GMFR	geometric mean fold rise
GMR	geometric mean ratio
GMT	geometric mean titer
ICD	informed consent document
ICH	International Council for Harmonisation
IRC	internal review committee
IST	independent statistical team
ITT	intent-to-treat
k el	first-order elimination rate constant
LLOQ	lower limit of quantitation
LOCF	last observation carried forward
LOD	limit of detection

Abbreviation	Term
LS	least-squares
LSM	least-squares mean
MAR	missing at random
MedDRA	Medical Dictionary for Regulatory Activities
miITT	modified intent-to-treat
MMRM	mixed-effects model with repeated measures
MNAR	missing not at random
N/A	not applicable
NOAEL	no-observed-adverse-effect level
PD	pharmacodynamic(s)
PK	pharmacokinetic(s)
PP	per-protocol
PPAS	per-protocol analysis set
PRO	patient-reported outcome
PT	preferred term
QTc	corrected QT
QTcF	corrected QT (Fridericia method)
qual	qualitative
RCDC	reverse cumulative distribution curve
RR	relative risk
SAE	serious adverse event
SAP	statistical analysis plan
SD	standard deviation
SGS	Statistical Guidance Standards
SOP	standard operating procedure
SUSAR	suspected unexpected serious adverse reaction
$t_{1/2}$	terminal phase half-life
TA	therapeutic area
TEAE	treatment-emergent adverse event
$T_{lag}$	time before the first concentration above the limit of quantification or above the first concentration in the interval
$T_{max}$	time to reach $C_{max}$
ULN	upper limit of normal
$V_z$	volume of distribution for extravascular dosing
$V_z/F$	apparent volume of distribution for extravascular dosing
WHO	World Health Organization
WHODD	World Health Organization Drug Dictionary
